**Early Withdrawal from the Study:**

- If a subject is lost to follow-up, or is unwilling to have a remote assessment performed, the subject will be considered an early withdrawal. Sites will be reminded to follow the procedures outlined in the protocol.

**Protocol Deviations:**

- All COVID-19 related protocol deviations will be reported and summarized in the Clinical Study Report.

## AMENDMENT HISTORY

Not applicable

## ABBREVIATIONS

AE	adverse event
ATC	anatomic and therapeutic Class
BMI	body mass index
BSA	body surface area
CI	confidence interval
CRF	case report form
CSR	Clinical Study Report
CV	coefficient of variation
DMC	Data Monitoring Committee
DPS	Data Presentation Specifications
ECG	electrocardiogram
eCRF	electronic case report form
FAS	full analysis set
FDA	Food and Drug Administration
ICH	International Conference on Harmonization
IQ	interquartile
MedDRA	Medical Dictionary for Regulatory Activities
PD	pharmacodynamic
PK	pharmacokinetic(s)
SAE	serious adverse event
SAP	Statistical Analysis Plan
SD	standard deviation
SMQs	standardised MedDRA queries
TEAE	treatment-emergent adverse event
WHO	World Health Organization
WHO-DD	World Health Organization Drug Dictionary
ITT	Intention-to-Treat

## 1. INTRODUCTION

This is a continued access trial for subjects who have completed treatment in a clinical trial with ETR sponsored by or in collaboration with Janssen Research & Development, and who continue to benefit from the use of ETR.

This statistical analysis plan (SAP) for the TMC125-TiDP35-C239 describes the statistical analysis for subject information and safety data.

### 1.1. Trial Objectives

The primary objective of the trial is to continue to provide ETR to subjects who previously received ETR in a clinical trial and continue to benefit from the use of ETR, in countries where ETR is not commercially available for the subject's indication, is not reimbursed, and cannot be accessed through another source (e.g. access program or government program), or where the subject is not eligible for ongoing trials/programs with ETR.

### 1.2. Trial Design

At the baseline visit, inclusion/exclusion criteria will be checked to confirm eligibility. Once eligibility criteria are met, subjects will either continue on the ETR dose they have received in the previous ETR trial or on an adjusted dose if deemed necessary by the investigator. For pediatric subjects, ETR dose adjustment will be based on weight using the dosing guidelines provided.

Assessment visits are recommended according to local generally accepted standard of care, but not less frequent than every three and six months for pediatric and adult subjects respectively. Adverse events leading to discontinuation or treatment interruption, adverse events at least possibly related to treatment with ETR, serious adverse events, and pregnancies will be recorded at each visit. In addition to the assessments described in the flowchart, additional assessments not included in this protocol can be done locally at the investigator's discretion as per local standard of care.

Treatment will be continued until one of the following criteria is met: the investigator determines that the subject no longer benefits from ETR treatment (e.g., based on viral load); treatment limiting toxicity; loss to follow-up; patient withdrawal of consent; pregnancy; termination of the program by the Sponsor; ETR becomes commercially available for the subject's indication, is reimbursed, or can be accessed through another source (e.g. access program, government program) in the region the subject is living in, whichever occurs first. A diagram of the study design is provided below in [Figure 1](#).

**Figure 1: Schematic Overview of the Study**

Type of Visit	Baseline a	Treatment period			Follow-up
Time of Visit	Day 1	Every 3 months for pediatric	Every 6 months for adult subjects	Final / withdrawal visit c	4 weeks after withdrawal
Informed Consent/Assent g	X				
Demographic data d	X				
Height h , Tanner staging h	X			X	
Weight	X	X	X		
Urine pregnancy test, if applicable e	X	X	X	X	
Inclusion/exclusion criteria	X				
Dispensation of investigational medication	X	X	X		
Drug accountability		X	X	X	
Collection of the following AEs f : - AEs considered to be at least possibly related to ETR; - AEs leading to discontinuations or treatment interruption;	X	X	X	X	X

- a Subject will rollover from another trial. Baseline visit will coincide with the last visit of the previous trial. Assessments and results from the last visit of the previous trial will be used for the Baseline Visit of this trial.
- b Only for subjects who drop out of the study due to the occurrence of a (S)AE.
- c Any AE event ongoing at the end of treatment should be followed up until satisfactory clinical resolution or stabilization at the investigator's discretion, according to the local standard of care.
- d Including Subject ID from feeder trial.
- e Urine pregnancy test for females of childbearing potential only.
- f Other AEs will only be collected if required per local regulations.
- g Informed assent only applicable to pediatric subjects.
- h Only applicable to pediatric subjects.

### 1.3. Statistical Hypotheses for Trial Objectives

N/A

### 1.4. Sample Size Justification

No formal sample size calculation has been performed. The trial is not set up to show a specific statistical hypothesis but to provide ETR to subjects who previously received ETR in a clinical trial sponsored by Janssen Research & Development, and continue to benefit from the use of ETR, in countries where ETR is not commercially available to subjects, is not reimbursed, and is not accessible through another source (e.g. access program or government program), or where the subject is not eligible for ongoing trials/programs with ETR. Data from this trial may be included in Safety Updates.

### 1.5. Randomization and Blinding

Since this is an open-label trial, blinding procedures are not applicable.

## 2. GENERAL ANALYSIS DEFINITIONS

### 2.1. Analysis Sets

Intent-to-treat (ITT) population: the set of all subjects who have taken at least 1 dose of ETR, regardless of their compliance with the protocol and adherence to the dosing regimen.

#### 2.1.1. Safety Analysis Set

All safety results will be presented for the ITT population.

### 2.2. Study Day and Relative Day

Study Day 1 or Day 1 refers to the start of the first study agent administration. All safety assessments at all visits will be assigned a day relative to this date.

Study day or relative day for a visit is defined as:

- Visit date - (date of Study Day 1) +1, if visit date is  $\geq$  date of Day 1
- Visit date - Date of Day 1, if visit date < date of Day 1

There is no 'Day 0'

### 2.3. Baseline and Endpoint

Baseline is defined as the last observation prior to the start of the first study agent administrations.

### 2.4. General Analysis Rules

- Data of adult and pediatric subjects will be analyzed separately. For the statistical analysis of TMC125-C239, a pediatric and adult subject will be defined as a subject who entered the previous trial at age < 18 and  $\geq$  18 years old respectively. Subjects who turn 18 while in the

previous trial or in TMC125-C239 will be considered as pediatric subjects for the statistical analysis.

- Continuous data will be summarized by descriptive statistics, including number of subjects (N), mean, standard deviation (SD), median, and range (minimum; maximum).
- The minimum and maximum will be presented to the same number of decimal places as the original data. The mean, median and 95% CI will be rounded to one additional decimal place than the original data, while SD will be approximated to two additional decimal places.
- If a count is 0, the percentage (0%) should not be displayed. The 0 count will be displayed, but the corresponding percentage should be omitted.
- The percentages (%) in tables will be presented to 1 decimal place unless the sample sizes for the percentages are small enough to warrant presenting as integers.

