## PROTOCOL AMENDMENTS

### **Amendment GEN-III (This document)**

**The overall reason for the amendment:** The aim of this roll-over study is to provide continued access to etravirine (ETR) for adult and pediatric subjects who continue to benefit from the use of ETR and who live in a country where ETR is either not commercially available, not reimbursed, or cannot be accessed through another source. As of this amendment, the follow-up in this study will be simplified for the reasons outlined below.

ETR is approved since 2008 in adults and since 2012 in children as of the age of 6 years and has a well-established safety profile. The collection of additional data in Study TMC125-C239 is unlikely to provide substantial additional information on ETR or to impact the risk-benefit assessment. The TMC125-C239 is a roll-over study that has been ongoing since December 2009 and provides already substantial long-term safety information on ETR. The parent trials TMC125-C206 and TMC125-C216 (in adults) ended in August 2008, after which the subjects were able to roll-over in the TMC125-C217 trial and subsequently into this roll-over study. Parent trial TMC125-C213 (in subjects aged 6 to 18 years) ended in August 2011. The parent trial TMC125-C234 (or IMPAACT trial P1090), conducted in subjects aged 1 to 5 years, is still ongoing and subjects still in this trial are expected to roll-over to Study TMC125-C239. By the time of entry in Study TMC125-C239, most of these subjects will have completed 48 weeks of ETR treatment plus an additional few years (up till 5 years) of follow-up in the parent trial. Hence, the subjects from Study TMC125-C239 have been on ETR for a significant amount of time. Therefore, the long-term safety of ETR has been properly assessed in these subjects, thereby allowing the study follow-up to be simplified for all subjects in this roll-over study.

As of this amendment, ETR will continue to be provided through this study until the subject can be switched to locally available ETR-based treatment regimens (ie, commercially available and reimbursed, or accessible through another source [eg, access program or government program]) or to local standard of care, as appropriate.

Furthermore, subjects aged 2 years and older are allowed to roll-over from parent trial TMC125-C234 and dosing instructions are added for pediatric subjects receiving another dose than provided in the dosing chart.

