## 1.2 Definition of Terms

Pediatric subjects      subjects who are at age < 18 years old at the Baseline Visit in this trial

Adult subjects          subjects who are at age  $\geq$  18 years old at the Baseline Visit in this trial

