### **5.7.3 STATISTICAL ANALYSIS**

Data of adult and pediatric subjects will be analyzed separately. For the statistical analysis of TMC125-C239, a pediatric and adult subject will be defined as a subject who entered the current trial at age < 18 and  $\geq$  18 years old respectively. Final analysis will be done once all subjects have completed the Final/Withdrawal Visit. After termination of data collection in the CRF (see [Figure 1](#)), no additional statistical analysis will be performed.

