## **8 DATA QUALITY CONTROL/ASSURANCE**

The trial is to be monitored by the sponsor or representative.

Shortly before the trial starts, the monitor meets with the investigator and all staff involved to review the procedures regarding trial conduct and recording the data on the CRF. During the trial, the investigator shall permit the monitor to verify the progress of the trial at the centre as frequently as necessary. The investigator shall make the CRFs available, provide missing or corrected data and sign the CRFs. Key data transcribed onto the CRFs, such as the subject's sex,

date of birth, assessment dates, test results, etc., are to be reviewed against source documents. Personal information is to be treated as strictly confidential and is not to be made publicly available. Any inconsistency between source data and data recorded on the CRF is to be corrected.

After termination of data collection (see [Figure 1](#)), all visits and assessments will be performed per local standard of care and documented in the subject's medical records only. Data will no longer be recorded in the CRF.

The sponsor will ensure that appropriate Quality Control (QC) steps are included into the different clinical processes to guarantee adequate protection of the trial subjects and quality of the data.

An independent Quality Assurance (QA) department, regulatory authorities and/or IECs/IRBs may review this trial. This implies that auditors/inspectors will have the right to inspect the trial centre(s) at any time during and/or after completion of the trial and will have access to source documents, including the subject's file. By participating in this trial, investigators agree to this requirement.

For any data transfer, measures will be undertaken to protect subject data handed over against disclosure to unauthorized third parties and subject confidentiality will be maintained at all times.

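### SAP 2.4 keeps subjects in the pediatric group after they turn 18, on an entry date that differs from the protocol's, and no planned table separates their adult-age follow-up

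*SAP*

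**What the plan says.** **Grouping rule, SAP.** SAP 2.4 states that "a pediatric and adult subject will be defined as a subject who entered the previous trial at age < 18" (adult if 18 or over). It then says that subjects who turn 18 during the previous trial or during C239 "will be considered as pediatric subjects for the statistical analysis".

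**Grouping rule, protocol.** Protocol 5.7.3 has "a pediatric and adult subject will be defined as a subject who entered the current trial at age < 18". Protocol 1.2 agrees and defines pediatric subjects as "subjects who are at age < 18 years old at the Baseline Visit in this trial".

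**Length of follow-up.** The rationale for Amendment GEN-III calls C239 a "roll-over study that has been ongoing since December 2009". It also says "Parent trial TMC125-C213 (in subjects aged 6 to 18 years) ended in August 2011". Treatment has no fixed duration. Under Amendment III (22 July 2019), the next planned visit of an ongoing subject is the last with CRF data (Protocol 5.1.1).

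**Outputs.** SAP 7.1 tabulates AEs for pediatric subjects, adult subjects and overall. SAP 7.2 summarises weight by visit for the same two groups, and the pediatric windows continue without an upper limit. SAP 5.4 declares extent of exposure not applicable. Nothing in the SAP 7.3 output list is specified by age at the event.

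**The concern.** Both documents choose to analyse children and adults separately, and both say that the data may go into Safety Updates. A reader of the pediatric columns will naturally take them as describing exposure in childhood and adolescence. Under SAP 2.4 they describe people who were under 18 when they entered an earlier trial, whatever their age when the event occurred. A skin, hepatic or neuropsychiatric event at age 24 would appear in the pediatric column of the events-of-interest table, unmarked. Mean weight change from baseline would combine children who are still growing with adults who have stopped.

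With no exposure summary, a reader also cannot see how much pediatric-group time was spent at adult ages. The two documents also place some subjects in different groups. For a subject who turned 18 in the parent trial, every C239 observation is adult-age, yet the SAP reports all of it as pediatric.

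**Working it through.** The plan gives no figure to reproduce: it has no sample size calculation, age summary at exit or person-time. Two checks are possible.

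**1. Age ceiling (date arithmetic).** The inputs are the December 2009 start, the August 2011 end of the parent trial in subjects aged 6 to 18, and the Amendment III date of 22 July 2019. The day within each start month is my choice: 1 December 2009 and 31 August 2011.

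Maximum age under the protocol rule = 18 + (end of CRF data − C239 entry). Under the SAP rule, add the time spent in the parent trial. I assume 48 weeks (0.92 years); the documents do not give this duration for that parent trial.

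| C239 entry | Follow-up to 22 Jul 2019 | Ceiling, protocol rule | Ceiling, SAP rule | Entry age from which 18 is reached |
|---|---|---|---|---|
| Dec 2009 | 9.6 y | 27.6 | 28.6 | 8.4 |
| Aug 2011 | 7.9 y | 25.9 | 26.8 | 10.1 |

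One further 3-month visit raises the protocol-rule ceilings to 27.9 and 26.1. The last column applies to a subject who stayed until July 2019. Crossing 18 is therefore not confined to subjects who entered at 17.

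**2. Share of pediatric-group person-time at 18 or over (illustrative).** The documents give neither the number of children who rolled over nor their entry ages or exit times. Assumptions:
- Protocol rule: C239 entry age is uniform on 6 to 18.
- SAP rule: parent-trial entry age is uniform on 6 to 18, and C239 entry comes d = 0.92 years later.
- Exit hazard h per year is constant, and maximum follow-up is F years.

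Let B = 1/h − F·exp(−hF)/(1 − exp(−hF)), with B = F/2 when h = 0. Integrating over entry age gives:
- protocol rule: share = B/12
- SAP rule: share = (d + B)/12

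Example with F = 7.9 and h = 0: B = 3.95, so the shares are 3.95/12 = 33% and 4.87/12 = 41%. With h = 0.8: exp(−6.32) = 0.0018 and B = 1.25 − 0.014 = 1.236, so the shares are 10% and 18%.

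| F | h | Protocol rule | SAP rule |
|---|---|---|---|
| 7.9 | 0 | 33% | 41% |
| 7.9 | 0.2 | 25% | 32% |
| 7.9 | 0.8 | 10% | 18% |
| 9.6 | 0 | 40% | 48% |
| 9.6 | 0.2 | 28% | 36% |
| 9.6 | 0.8 | 10% | 18% |

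Across both rules the range is roughly 10% to 41% with F = 7.9, the follow-up of someone entering when the parent trial ended. The upper end reaches 48% only if every subject entered in December 2009 and none left. Under the same assumptions, the SAP rule always gives the larger share because it keeps subjects who were already 18 at C239 entry.

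**The case against.** Grouping by entry age is a stated convention in a descriptive access trial with no hypothesis. It keeps each subject in one denominator and gives a coherent account of long-term safety in people who started as children. Neither document says that the pediatric tables are meant to describe events in childhood only. This stands: the rule is disclosed and is not an arithmetic error.

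Exits may also be frequent. Treatment stops when ETR is commercially available for the subject's indication and reimbursed, or accessible elsewhere. The amendment rationale dates approval to 2008 in adults and 2012 in children from 6 years, and SAP 5.2 has a disposition category for switching to commercial supply. A constant hazard unrelated to age or approval has no source in the documents. This stands too, so the shares above illustrate scale and are not bounds.

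A reader might infer that the pediatric tables mainly describe adults, or that follow-up into the mid-twenties is typical. The documents do not support either reading. The ages are ceilings for the oldest, earliest and longest-followed entrants. The real share is unknown, and it stays below half in every setting shown. Nor are the analysed data open-ended: treatment may continue, but CRF collection closes at the Final/Withdrawal Visit.

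Finally, SAP 5.1 lists demographics for every subject, SAP 7.3 lists all AEs and events of interest, and SAP 2.2 assigns a relative day. Age at a single rare event could probably be reconstructed from these, although the listing columns are not specified. That helps with individual cases but does nothing for the summary tables.

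**Conclusion.** The point holds as a reporting weakness that is cheap to correct. SAP 2.4 explicitly puts follow-up after the 18th birthday into the pediatric group, and no planned summary separates or quantifies it. The SAP also conflicts with Protocol 1.2 and 5.7.3 on which entry date counts. Aligning the two would move subjects already 18 at C239 baseline into the adult group, but would leave the post-18 follow-up of everyone else unseparated.

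The date arithmetic supports a ceiling of about 26 to 28 years for a subject who entered C239 just under 18. The figure of roughly 10% to 41% of pediatric-group person-time rests entirely on assumed uniform entry ages, constant exit hazards of 0 to 0.8 per year, about 8 years of maximum follow-up and, for the SAP rule, 48 weeks in the parent trial. The actual share can be known only from the trial database.

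**What to change.** 1. **Definition.** Change SAP 2.4 to the protocol definition, age at entry to C239, and adjust the sentence on subjects who turn 18 accordingly.

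2. **Adverse events.** Keep the entry-age groups as the main presentation. Within the pediatric group, add a split by age at onset (under 18; 18 or over) to at least TSFAE01, TSFAE03 and TSFAE05 to TSFAE07. Give each age period its own denominators: the number of subjects observed in it and the person-years. Onset columns without these cannot be interpreted, and SAP 5.4 currently supplies no exposure. Show age at onset in the AE listings.

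3. **Weight.** Keep all weights of the pediatric group. Flag those measured at or after the 18th birthday, or summarise them separately. Ending the pediatric windows at 18 would drop later weights from every summary, because the adult tables cover only the adult group. It would also leave only the youngest entrants in the late windows.

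**Cost.** SAP wording, an age-at-onset flag and a simple person-time derivation; no new data. Protocol Part II, section 8 names among the key CRF data "date of birth, assessment dates, test results, etc., are to be reviewed against source documents", and section 1.4 has AE start dates on the CRF. The price is smaller cells and a rule for partial onset dates that span the 18th birthday; the partial-date rule in SAP 7.1 covers only treatment emergence.

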### 3. INTERIM ANALYSIS AND DATA MONITORING COMMITTEE REVIEW

There is no interim analysis planned for this study.

### 4. COVID RELATED DEVIATIONS

All COVID related deviations will be tabulated and listed.

### 5. SUBJECT INFORMATION

#### 5.1. Demographics and Baseline Characteristics

Table 01 presents a list of the demographic variables that will be summarized by pediatric and adult subjects separately as well as all combined for ITT analysis set.

**Table 01: Demographic Variables**

Continuous Variables	Summary Type
Age (years)	Descriptive statistics (N, mean, standard deviation [SD], median and range [minimum and maximum])
Height (cm)	
Weight (kg)	
Categorical Variables	
Sex (male, female)	Frequency distribution with the number and percentage of subjects in each category.

The demographics and baseline characteristics will be listed for all subjects.

#### 5.2. Disposition Information

The number of subjects in the following disposition categories will be summarized:

- Subject didn't fulfill all inclusion/exclusion criteria (screen failures)
- AE/HIV-related event/Cutaneous event/Rash (including death, abnormal lab values, current illnesses)

- Lost to follow-up
- Withdrew consent/assent
- Non-compliant
- Ineligible to continue the trial
- Investigator no longer thinks subject benefits from the ETR treatment
- Sponsor's decision
- Switch to commercially available medication
- Other

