## 2 FLOWCHART

### 2.1 Flowchart 1: Trial Follow-up

#### Up to and including Protocol Amendment 2:

| Type of Visit  | Baseline a | Treatment period                      |                                   |   | Follow-up visit b |
|--|-----------------------|---------------------------------------|-----------------------------------|---|------------------------------|
| Time of Visit  | Day 1                 | Every 3 months for pediatric subjects | Every 6 months for adult subjects | Final / Withdrawal visit c,i | 4 weeks after withdrawal     |
| Informed Consent/Assent g   | X                     |                                       |                                   | X j                          |                              |
| Demographic data d  | X                     |                                       |                                   |   |                              |
| Height h , Tanner staging h  | X                     |                                       |                                   | X                                       |                              |
| Weight   | X                     | X                                     | X                                 |   |                              |
| Urine pregnancy test, if applicable e   | X                     | X                                     | X                                 | X                                       |                              |
| Inclusion/exclusion criteria   | X                     |                                       |                                   |   |                              |
| Dispensation of investigational medication   | X                     | X                                     | X                                 | X j                          |                              |
| Drug accountability  |                       | X                                     | X                                 | X                                       |                              |
| Adherence Counseling   | X                     | X                                     | X                                 | X j                          |                              |

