| Collection of the following AEs f :
- AEs considered to be at least possibly related to ETR;
- AEs leading to discontinuations or treatment interruption;
- SAEs and pregnancies | X                     | X                                     | X                                 | X                                       | X                            |

a Subject will rollover from another (parent) trial. Baseline visit will coincide with the last visit of the previous (parent) trial. Assessments and results from the last visit of the previous (parent) trial will be used for the Baseline Visit of this trial.

b Only for subjects who drop out of the study due to the occurrence of a (S)AE.

c Any AE event ongoing at the end of treatment should be followed up until satisfactory clinical resolution or stabilization at the investigator's discretion, according to the local standard of care.

d Including Subject ID from parent trial.

e Urine pregnancy test for females of childbearing potential only.

f Other AEs will only be collected if required per local regulations.

g Informed assent only applicable to pediatric subjects.

h Only applicable to pediatric subjects.

i The next planned visit will be a Final/Withdrawal Visit for all subjects when discontinuing the trial or switching to simplified data collection as per Protocol Amendment 3. For subjects continuing the trial under Protocol Amendment 3, all subsequent visits and assessments will be performed per local standard of care and documented in the subject's medical records only, as described in [Flowchart 2: Simplified Trial Follow-up](#).

j Only applicable for subjects continuing the trial under Protocol Amendment 3.

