For ongoing subjects, the next planned visit after approval of amendment 3 will be a Final/Withdrawal Visit ([Figure 1](#)). During this Final/Withdrawal Visit, the informed consent will be signed, final assessments will be carried out and recorded in the CRF, and the study medication will be dispensed as described in [Flowchart 1: Trial Follow-up](#). For new subjects that roll-over from (parent) trial TMC125-C234 (IMPAACT P1090) after approval of amendment 3, the next planned visit will be a Baseline Visit ([Figure 1](#)). During this Baseline Visit, the informed consent will be signed and assessments will be performed per local standard of care and documented in the subject's medical records only.

For all new and ongoing subjects, all subsequent visits and assessments will be performed per local standard of care and documented in the subject's medical records only. Investigators will continue to report SAEs possibly related to ETR and pregnancies to the sponsor using regular pharmacovigilance reporting. This information will only be entered in the company safety repository.

For all new and ongoing subjects, if the subject exits the trial, the last visit will be a local standard of care visit but without dispensation of investigational medication.

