**As per Protocol Amendment 3:**

For ongoing subjects, the next planned visit will be a Final/Withdrawal Visit, which will be the last visit with data collection. For new subjects that roll-over from (parent) trial TMC125-C234 (IMPAACT P1090), the next planned visit will be a Baseline Visit which will be performed per local standard of care and documented in the subject's medical records only.

For all new and ongoing subjects, all subsequent visits and assessments will be performed per local standard of care and documented in the subject's medical records only. Investigators will continue to report SAEs possibly related to ETR and pregnancies to the sponsor using regular pharmacovigilance reporting. This information will only be entered in the company safety repository.

For all new and ongoing subjects, if the subject exits the trial, the last visit will be a local standard of care visit but without dispensation of investigational medication.

Treatment will be continued until one of the following criteria is met: the investigator determines that the subject no longer benefits from ETR treatment (e.g., based on viral load); treatment limiting toxicity; loss to follow-up; patient withdrawal of consent; pregnancy; termination of the program by the sponsor; an ETR-based treatment regimen becomes commercially available for the subject's indication and is reimbursed, or can be accessed

through another source (e.g. access program, government program) in the region the subject is living in, or subjects can be switched to local standard of care, as appropriate.

Details on the timing of the treatment and assessments are given in the flowchart (see Section 2).

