#### **5.7.3.1 Safety**

The safety of ETR will be summarized in terms of:

- Mortality
- All SAEs
- AEs leading to discontinuation
- AEs possibly related to ETR treatment

The number of and causes of deaths will be summarized.

The number of subjects who terminate treatment will be tabulated, and reasons for drug discontinuation will be summarized.

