### **5.4. Extent of Exposure**

Not applicable for this study

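### Does SAP 5.2 need a disposition row for subjects who finish CRF data collection but stay on etravirine under Amendment 3?

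*SAP*

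**What the plan says.** SAP 5.2 introduces its list with "The number of subjects in the following disposition categories will be summarized". The ten entries are screen failure; adverse, HIV-related or cutaneous event; lost to follow-up; consent or assent withdrawn; non-compliance; ineligibility to continue; no further benefit in the investigator's view; sponsor's decision; switch to commercial medication; and Other. The outputs are TDIS01 and LDIS01, given by title only in SAP 7.3. On exposure, SAP 5.4 says "Not applicable for this study".

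Protocol 5.7.3.1 requires that "The number of subjects who terminate treatment will be tabulated, and reasons for drug discontinuation will be summarized".

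Amendment 3 gives one visit two uses. Footnote i of Flowchart 1 reads "The next planned visit will be a Final/Withdrawal Visit for all subjects when discontinuing the trial or switching to simplified data collection". For ongoing subjects, protocol 5.1.1 says "the next planned visit will be a Final/Withdrawal Visit, which will be the last visit with data collection". The text for the simplified follow-up says that at this visit "final assessments will be carried out and recorded in the CRF, and the study medication will be dispensed as described in" Flowchart 1. In that flowchart the row "Dispensation of investigational medication" is marked at the Final/Withdrawal Visit with footnote j: "Only applicable for subjects continuing the trial under Protocol Amendment 3".

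**The concern.** The visit's name suggests that everyone who attends it has left, yet some attend only to move to simplified follow-up and go home with drug. The SAP has no row for them and no coding rule. If they were placed under Other or the sponsor-decision row, the table would mix people still on etravirine with people who stopped, and the termination count would be too high. Other is a poor place for them in any case, because real exits without a named row, such as a move to local standard of care, may also land there.

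Little else in the output list would reveal the mistake. No exposure table is planned. Outside disposition, only TSFAE06 and LSFAE06 deal with stopping treatment, and they cover adverse events alone. The SAP also looks out of step with Amendment 3. It provides for COVID deviations, so it is later than the amendment of 22 July 2019, yet its design text and Figure 1 describe the earlier scheme. In a trial whose purpose is continued access, who stopped and who stayed on drug is worth reporting correctly.

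**Working it through.** The plan gives no figure to reproduce: there is no sample size calculation, and neither the number treated nor the number continuing is stated. The check compares the passages and then bounds the count.

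**Rows.** 1 screen failure + 8 stopping reasons + 1 Other = 10. Rows for subjects continuing etravirine = 0. The gap is real.

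**Is any rule wrong?**
- SAP 5.2 gives no instruction that puts a continuing subject under Other or the sponsor-decision row.
- Protocol 5.2.5 asks for the date and reason of discontinuation on the CRF and mentions the CRF termination section in that same paragraph. It then sends Amendment 3 terminations to a separate paper form. A subject who has not discontinued has no reason to enter.
- Protocol 5.7.3 runs the final analysis once all subjects have had the Final/Withdrawal Visit, so no ongoing subject is still awaiting a last CRF visit at that point.
- Subjects who roll over from the C234 trial after the amendment have their visits documented in medical records only (protocol 5.1.1), so they do not enter the CRF-based count.

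**The count.** Let N be treated subjects with CRF data (the SAP 2.1 population), D those who stopped etravirine by their last CRF visit, and C = N − D those continuing.
- Continuing subjects given no stopping reason: the reasons sum to D. The required count is correct, and C = N − D follows by subtraction.
- All continuing subjects coded as stopped: the reasons sum to D + C = N.

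The total read from the table therefore lies between D and N, and the reading supported by protocol 5.2.5 gives D.

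**Worst case, on an assumed share.** With c = C/N, the ratio of shown to true is N/D = 1/(1 − c).
- c = 5%: 1/0.95 = 1.05
- c = 25%: 1/0.75 = 1.33
- c = 50%: 1/0.50 = 2.00

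These shares are assumptions with no basis in the documents. Each ratio also requires every continuing subject to be miscoded and the reader to add the affected row into a termination total. Even then only the row used is distorted; the other reasons stay right.

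**Can continuing subjects be identified?** Footnote j marks three items at the Final/Withdrawal Visit that apply to them alone: consent, dispensation and adherence counselling. Consent is the firmest marker. Dispensation alone is weaker, because protocol 5.3.8 keeps it on accountability forms and the COVID-19 appendix allows remote visits and shipment to the home.

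**The case for a change.** The best case for a change is that it would cost one row and one sentence, while silence leaves the total anywhere between D and N. The double use of the visit invites a site or programmer to record a reason for everyone who attends, and the protocol asks explicitly for the termination count. Neither the CRF termination page nor the TDIS01 shell is in the documents, so it cannot be shown that continuing subjects are kept apart.

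Part of this stands. The category is unwritten, and if the termination page were completed for continuing subjects, their entries would have to be separated before the table was read. But the same absence means it cannot be shown that they are mixed in. The harm needs a coding choice that contradicts the subject's own record of renewed consent and fresh supply. An analyst who sees subjects with no stopping reason would show them as continuing, as the Amendment 3 text describes, and would need no new data to do so. The outdated design text in SAP 1.2 is background and sets no rule for disposition.

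**Conclusion.** The concern does not call for a change. SAP 5.2 leaves one category unnamed, but followed as written it does not produce a wrong number: the stopping reasons count true stops, and continuing subjects are the remainder of the treated total. The error is zero on that reading. It would be positive, by an unknown amount, only if people still receiving etravirine were coded as having stopped. The conclusion assumes that a reason is recorded for every true stop, as protocol 5.2.5 requires, and that continuing subjects either have no termination reason on the CRF or can be recognised by their Amendment 3 consent.

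The stakes are limited. The trial tests no hypothesis, the count is one descriptive item within safety, stops due to adverse events have their own table and listing, and no adverse event percentage depends on this row. Showing continuing subjects on their own line, with TDIS01 labelled as of the Final/Withdrawal Visit, is ordinary table programming and needs no amendment to the plan.
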